### C. Study Design and Research Methods

This is a single-blind, randomized controlled trial with 100 Veterans scheduled to have unilateral primary TKA at the Denver VAMC or UCH. The two study arms will be physical activity behavior-change (PAB) and attention control (CTL). Researchers collecting data will be blinded to group assignment.

Conventional TKA rehabilitation at the Denver VAMC and at the University of Colorado Hospital consists of a total of 20-24 combined inpatient and outpatient visits. To ensure the total number of rehabilitation interactions in the proposed study is comparable to conventional rehabilitation, a total of 14 conventional rehabilitation visits (inpatient and outpatient) will be combined with 10 telerehabilitation sessions for 24 total rehabilitation interactions in both groups.

#### *Physical Activity Behavior-Change (PAB) Intervention*

The PAB intervention will be integrated into the current evidence-based conventional rehabilitation following TKA (Figure 4 and Appendix 6). The PAB intervention will begin at the start of Week 3 Post-TKA and consist of a total of 10 participant/therapist telerehabilitation sessions (30 minutes each). The telerehabilitation sessions will occur using video-based interactions with computer tablets provided by the VA, to ensure Veteran confidentiality standards are met. One week prior to the first PAB session, a VA WOC physical therapist who specializes in behavior-change intervention will perform a home visit to provide each PAB participant with a Fitbit wearable sensor and feedback tablet for the Fitbit, along with the telerehabilitation tablet. The therapist will also perform a home-safety check (Appendix 7). The Fitbit wearable sensor is designed specifically to provide user visual physical activity feedback through an application on the feedback tablet. Fitbit use instructions will be provided verbally and in written form (Appendix 8). The Fitbit application will provide the participant feedback on the number of steps he/she has taken during daily living activity and progress toward physical activity goals.

The first week of using the Fitbit activity sensor will be an accommodation period for the participant to interact with the equipment and establish his/her baseline for self-monitoring daily step count. The telerehabilitation tablets will provide the means for remote video interactions between the participant and therapist. The participant will then work with the therapist in the 30-minute video-based telerehabilitation sessions on participant-tailored functional action plans. Each plan will be based on the tailored physical activity feedback provided by the Fitbit sensor. The 10 PAB sessions will be tapered between Week 3 and Week 14 Post-TKA: Week 3 twice weekly (2 sessions), Weeks 4-9 once weekly (6 sessions), and Weeks 10-14 once every other week (2 sessions). The therapist will systematically address the seven components of PAB intervention: education, self-monitoring, feedback, barrier and facilitator identification, problem solving, action planning, and encouragement (Table 3 and Appendix 6) with varying levels of time focused on each of these components as the intervention progresses. The therapist will also document health visits, falls, knee pain, and medication changes at each telerehabilitation session.

Table 2. PAB Intervention Overview

Intervention Technique	Progression from Therapist Coaching to Participant Self-Management	
Education	Therapist delivers education topic* (e.g., Self Monitoring, Problems Solving, Identifying Barrier/Facilitators, Action Plans)	Participant reports most important information learned.
Self Monitoring	Therapist guides participant in tracking daily step count patterns since last visit.	Participant tracks daily step count trends weekly and over the course of intervention.
Tailored Feedback	Therapist leads collaborative review of step count data for action plan goal setting.	Participant leads review of step count and other physical activity goals.
Barrier / Facilitator Identification	Therapist guides participant to identify barriers/facilitators of goal attainment.	Participant self-identifies barriers and facilitators for goal attainment.
Promotion of Problem Solving	Collaborative generation of solutions to overcome barriers to goal attainment.	Participant generates solutions to identified barriers to goal attainment
Action Planning	Collaborative activity goal generation. Therapist guides, using 3% increase from daily steps from previous week target.	Participant-led weekly goal generation. Therapist ensures independence in action planning.
Encouragement	Therapist reviews plan for the next week, while encouraging participant on successes attained toward improved physical health.	Participant leads the review of the plan for upcoming week.

\* Each week will have a specific 'take home' message linking physical activity and movement behavior to health. Messages will be brief and based on research evidence.

#### *Control (CTL) Intervention*

The CTL group will perform all of the conventional inpatient and outpatient visits following TKA, just as the PAB group (Appendix 8). Some conventional outpatient visits will occur at the Colorado Springs VA Clinic. CTL group telerehabilitation sessions will match the frequency and duration of PAB group. The CTL group sessions will focus on education related to non-behavioral aspects of health. Education will be systematically delivered by the

therapist using the telerehabilitation tablets with the following topics: Sessions 1-2) Pain Management; Sessions 3-4) Home Safety; Sessions 5-6) Diet; Sessions 7-8) Medication Management; Sessions 9-10) Falls & Fractures (Appendix 8). In addition, the therapist will document health visits, falls, knee pain, and medication changes at each telerehabilitation session. The participant/therapist video-based telerehabilitation sessions will be semi-scripted with the same duration (30 min.) and same tapered schedule as the PAB group. In this manner, the study design controls for attention and volume of rehabilitation intervention. Telerehabilitation sessions will be conducted by therapists who may be physically present on the Anschutz Medical Campus. Some telerehabilitation sessions from both the PAB group and the CTL group may be audio recorded for interventionist fidelity checks.

#### *Data Collection and Outcomes*

Preoperative testing will occur 2 weeks prior to TKA (PREOP). Postoperative testing will occur midway through the PAB intervention (POST1), at the end of PAB intervention (POST2), and 24 weeks after PAB intervention (approximately 9-months after TKA) (POST3). The POST1 test will assess early between-group responses to intervention, while the POST2 test will assess group differences at intervention end (Primary End Point). The POST3 test is critical, as a key component to assessing success of behavior change is the long-term persistence of behavior change. Each test session will include the standardized procedures described in the next sections. Importantly, all test sessions occur at participant homes, to eliminate time and travel burdens for the participants and minimize barriers for rural participants. The 30-Second Chair Stand Test and Timed-up-and Go may be conducted remotely via video call and surveys may be conducted via phone/video call or through REDCap. Semi-structured interviews will occur following randomization, and again following the POST2 assessment period. Up to 20 participants will be randomly selected from the PAB group to have at least 10 participants participate in semi-structured interviews at both time points. An interview guide will be used with questions regarding the PAB program, perceptions of barriers and facilitators to physical activity, and perceptions of participation in everyday life. Depending on participant preference the interview can occur in-person, over the phone, or via an audio-visual application. All interviews will be audiorecorded and transcribed verbatim by a research team member or an approved transcription service.

#### **D. Description, Risks and Justification of Procedures and Data Collection Tools:**

Anticipated adverse events include medical complications due to the complex medical conditions of the older Veteran population and the surgical procedure prior to the intervention. Although no increase rate of falls was seen in the pilot study, we also anticipate increased exposure to fall risk due to increased exposure to physical activity. As such, a Safety Officer, [name], experienced in clinical trial safety outcome measures will meet with the PI quarterly to review study progress and adverse events. Fall risk will be monitored using the TUG test and Falls Efficacy Scale-International (FES-I) at all test points (PREOP, POST1, POST2, POST3). Also, occurrence of falls will be recorded at each weekly visit for both the PAB and CTL groups. Fall occurrences (injurious and non-injurious) and other adverse events will be reported on a quarterly basis to the Safety Officer. The incidence of falls, defined as “inadvertently coming to rest on the ground, floor or other lower level, excluding intentional change in position,” will be of particular focus. All study-related falls (possibly, probably, or definitely) will be tracked. If the total number of falls reaches 5, the Safety Officer will review incidence by group. If the number of injurious falls for the intervention group exceeds that of the control group by 5 (5% of enrollment) at any time, the study will be suspended until an evaluation of study relatedness for each incidence is performed by the Safety Officer. Also, some questions may make subjects feel uncomfortable. There is a rare but significant risk of loss of confidentiality. There are also risks that are unknown at this time.

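### No scheduled collection of fall occurrence is described in either arm between the last telerehabilitation session (Week 14) and POST3 (Week 38), although the between-arm injurious-fall rule has no time limit

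*Combined protocol and SAP*

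**What the plan says.** Three places in the protocol deal with recording falls.

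- Section IV.C, PAB intervention: "The therapist will also document health visits, falls, knee pain, and medication changes at each telerehabilitation session". For timing: "The 10 PAB sessions will be tapered between Week 3 and Week 14 Post-TKA". There are two sessions in Week 3, one a week in Weeks 4 to 9, and one every other week in Weeks 10 to 14.
- Section IV.C, control intervention: "the therapist will document health visits, falls, knee pain, and medication changes at each telerehabilitation session", on the same schedule as PAB.
- Section IV.D, risks: "occurrence of falls will be recorded at each weekly visit for both the PAB and CTL groups". The weekly visit is not defined.

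Section IV.D also assigns TUG and FES-I to all four test points, as monitoring of fall risk. It sends injurious and non-injurious falls, with other adverse events, to the Safety Officer every quarter. It adds: "All study-related falls (possibly, probably, or definitely) will be tracked". Neither the reporting nor the tracking sentence has an end date or a collection method.

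Two triggers follow. When total falls reach five, the Safety Officer looks at incidence by group. The second is between arms: "If the number of injurious falls for the intervention group exceeds that of the control group by 5 (5% of enrollment) at any time". Meeting that condition suspends the trial until relatedness has been evaluated for each event.

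Data Collection and Outcomes places POST3 24 weeks after the intervention. The SAP gives the last time point as 38 weeks after surgery and does not mention falls.

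**The concern.** A rule that compares arms needs falls to be found equally well in both arms for as long as the rule is in force. Here the scheduled questioning stops when therapist contact stops, but the rule does not.

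The uncovered period is also the one to which the protocol's own reasoning points. Section IV.D anticipates more exposure to falls because participants will be more active. Hypothesis 1.1 expects the difference in activity to persist at POST3. If the intervention works, the added exposure continues for about 24 weeks without a therapist contact at which falls are asked about.

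In that period the rule would depend on whatever participants happen to volunteer. Reporting habits could differ by arm: control Sessions 9 and 10 are on falls and fractures, which could change what control participants later report. The documents do not allow the size or direction of any such difference to be judged.

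**Working it through.** **Timeline.** Inputs are the Week 3 to Week 14 session window (PAB section), POST3 at 24 weeks after the intervention (Data Collection and Outcomes), and the 38-week final time point (SAP).

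- Week of POST3: 14 + 24 = 38, which agrees with the SAP.
- Weeks after the session window: 38 − 14 = 24; 24/38 = 63%.
- Session count: 2 + 6 + 2 = 10, as stated. Sessions are not weekly in Weeks 10 to 14, so the weekly visit does not match the session schedule there.

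**What each contact collects.**

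| Contact | Weeks | Fall occurrence asked? |
|---|---|---|
| Telerehabilitation sessions, both arms | 3–14 | Yes |
| Weekly visit (undefined) | Not stated; no weekly contact described after Week 14 | Yes |
| POST1, POST2, POST3 | 8, 14, 38 | Not listed; TUG and FES-I only |
| Quarterly report to the Safety Officer | No end date | Passes on what was collected; no method given |

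Reading the weekly visit to include conventional rehabilitation visits does not close the gap, since none is described for Weeks 15 to 38.

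**Illustration for the between-arm rule.** The documents give no injurious-fall rate, so the rates here are assumptions: 0.1, 0.2 or 0.3 per person-year in control, constant over time. Falls are treated as independent Poisson events, all 50 per arm stay in follow-up, and no fall is learned of outside scheduled collection. The rule is taken as met when PAB minus control first reaches 5.

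Exposure per arm is 50 × 12 = 600 person-weeks for Weeks 3 to 14, and 50 × 36 = 1,800 for Weeks 3 to 38. Expected control falls = rate × person-weeks / 52. At 0.2 this is 0.2 × 600/52 = 2.3, against 0.2 × 1,800/52 = 6.9. The probability of ever reaching +5 comes from a random walk over the merged fall events.

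| Assumed control rate | PAB rate doubled: 12 wk | PAB rate doubled: 36 wk | Equal rates: 12 wk | Equal rates: 36 wk |
|---|---|---|---|---|
| 0.1 | 5% | 43% | 0.3% | 6% |
| 0.2 | 23% | 79% | 2.5% | 18% |
| 0.3 | 43% | 91% | 6% | 27% |

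Under these assumptions the rule is much less likely to register a doubling on session data alone. With equal rates, longer collection also makes a chance crossing more likely.

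**The case against.** The strongest reply is that active questioning during the intervention, followed by ordinary adverse-event reporting, is a defensible design. The commitments to track falls and report quarterly are open-ended, staff have contact with participants at POST3, and the appendices are not in the supplied text, so a fall form used later cannot be excluded. This stands as far as it goes: some post-Week 14 falls may well reach the Safety Officer. It does not supply a method or schedule, or any assurance that the two arms are asked alike.

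Several stronger readings are tempting but not supported.

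- *The rule has no data after Week 14.* The open-ended tracking and reporting rule this out. What is missing is scheduled collection. With staggered entry, session data from some participants could also arrive while others are in follow-up; the gap is per participant.
- *Falls are collected only at telerehabilitation sessions.* That is an inference about the undefined weekly visit.
- *A relatedness filter applied by unblinded staff depresses the control count.* The documents do not say who makes the judgement behind the tracking sentence. The one named assessor is the Safety Officer, who evaluates relatedness after the suspension trigger is met, and that trigger carries no relatedness condition.
- *The fall counts contradict each other.* Recording all falls and tracking the related ones can coexist, and the two triggers deliberately use different counts. The wording does leave unclear which falls enter the total.
- *A large number of missed falls can be set against the five-fall review.* That is the wrong trigger. At an assumed 0.3 to 1.0 falls per person-year, session data alone cover 100 × 12/52 = 23 person-years and would yield about 7 to 23 falls, enough to prompt that review. Calling later falls missed also assumes that none is volunteered.

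**Conclusion.** The point holds as a gap in safety ascertainment. For 24 of 38 post-surgical weeks (63%), no scheduled collection of fall occurrence is described in either arm, while the between-arm rule has no time limit and the activity difference is expected to persist. Followed as written, the rule would rest on unsolicited reports in that period.

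The 63% comes from the documents' own schedule. The probabilities above rest on assumed rates, full retention and no volunteered reports; they show that the gap could matter to the rule and do not estimate what happened. The conclusion also assumes that no appendix contains a later fall form; if one does, a cross-reference in Section IV.D settles the point.

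The gap should be corrected. It does not touch the step-count analysis.

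**What to change.** In Section IV.D:

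1. Add one fall-occurrence question at POST3 in both arms, using the fall definition already given there and recording whether the fall was injurious.
2. Add a short REDCap or phone fall query at fixed intervals between Week 14 and POST3, identical in both arms. Feed both sources into the existing quarterly review.
3. Replace the reference to a weekly visit with the contacts at which falls are actually recorded.
4. State which count feeds each existing trigger, reconciling the sentences on recorded, total and study-related falls. Keep the two triggers separate and leave their thresholds alone.

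The cost is a few questions through channels the protocol already uses, slight participant burden, and some recall error over the longer intervals. The Safety Officer should know that fuller collection gives chance differences more time to build up.

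The SAP is written in the past tense. If follow-up is already complete, the report should say how falls were ascertained before and after Week 14 and show counts by arm for the two periods separately.

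### The only stated route for falls to the Safety Officer is a quarterly report, although two fall triggers depend on that officer acting between reports

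*Combined protocol and SAP*

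**What the plan says.** Protocol section IV.D (Description, Risks and Justification of Procedures and Data Collection Tools) sets out the whole fall-monitoring scheme.

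- **Recording.** "occurrence of falls will be recorded at each weekly visit for both the PAB and CTL groups". The PAB intervention section names the recorder: "The therapist will also document health visits, falls, knee pain, and medication changes at each telerehabilitation session". The Control (CTL) Intervention section gives the therapist the same task.
- **Reporting.** "Fall occurrences (injurious and non-injurious) and other adverse events will be reported on a quarterly basis to the Safety Officer". The Safety Officer also "will meet with the PI quarterly to review study progress and adverse events".
- **First trigger.** "If the total number of falls reaches 5, the Safety Officer will review incidence by group".
- **Second trigger.** "If the number of injurious falls for the intervention group exceeds that of the control group by 5 (5% of enrollment) at any time", then "the study will be suspended until an evaluation of study relatedness for each incidence is performed by the Safety Officer".

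The Statistical Analysis Plan does not mention safety monitoring. The appendices that the protocol cites are not part of the supplied text.

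**The concern.** Both triggers are defined by events, and both require the Safety Officer to do something: review incidence by group, or judge relatedness while the study is suspended. The stated flow of information to that officer follows the calendar. A rule that can fire on any day works as intended only if the person who must act on it hears of the events soon after they happen.

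What is at stake is participant safety. Section IV.D itself expects more exposure to fall risk as activity rises, and this is the only suspension rule in the documents. Participants begin PAB at Week 3 after surgery and finish at Week 14. A wait of a full quarter could therefore outlast a participant's entire course of sessions.

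**Working it through.** **The plan's own figure.** The suspension threshold is given as 5 injurious falls, or 5% of enrollment. Planned enrollment is 100 (section IV.B), and 5/100 = 5.0%, so the figure reproduces. The threshold itself is not in question.

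**Order of the two triggers.** If all falls count, a PAB excess of 5 injurious falls needs at least 5 falls in total. The by-group review therefore falls due at or before suspension. The two coincide only if the first five falls are all injurious and all in PAB. The review is thus usually the earlier safeguard, but it relies on the same officer and the same stated reporting route.

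**Wait from record to Safety Officer, if the quarterly report is the route.** Assume reports 13 weeks apart and a crossing equally likely at any point between them.

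- Maximum wait = 13 weeks.
- Mean wait = 13/2 = 6.5 weeks.

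**Wait with prompt forwarding.** Take 3 days as an example of a few days.

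- Wait after recording = 3/7 = 0.43 weeks.
- Mean saving = 6.5 − 0.43 = 6.07 weeks.

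**Delay before a fall is recorded.** This comes before either route, so it does not change the saving. Counting weeks from the start of Week 3, the PAB schedule puts sessions at 0, 0.5, 1, 2, 3, 4, 5 and 6, with two more in Weeks 10–14 whose exact dates are not given. Mean delay to the next session = Σ(gap²/2) ÷ time of last session.

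| Assumed last two sessions (weeks) | Mean delay (weeks) | Longest gap (weeks) | Fall to officer, quarterly: mean / max (weeks) | Fall to officer, 3-day forwarding: mean / max (weeks) |
|---|---|---|---|---|
| 7, 9 | 5.25/9 = 0.58 | 2 | 7.08 / 15 | 1.01 / 2.43 |
| 8, 10 | 6.75/10 = 0.675 | 2 | 7.17 / 15 | 1.10 / 2.43 |
| 9, 11 | 9.25/11 = 0.84 | 3 | 7.34 / 16 | 1.27 / 3.43 |

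These figures cover falls during the session period only. Follow-up runs a further 24 weeks after the intervention (POST3), when no sessions are scheduled.

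**What cannot be computed.** The documents give no rate of injurious falls by arm. Neither the probability of a crossing nor the number of further falls during a wait can be estimated from them.

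**The case against.** The strongest reply is that the quarterly report and meeting are routine review, and that the triggers are exceptions to it. A reader might infer that the plan makes the triggers wait for the next quarterly report, or that the suspension rule cannot operate. The text supports neither reading. It says the suspension rule applies at any time. Therapists in both arms record falls at every session, so the team could act within days. A reader might also infer that nobody would be counting falls by arm. A between-arm rule implies such a count, and section IV.D says "All study-related falls (possibly, probably, or definitely) will be tracked". The name of the person keeping the count is unstated, and on its own that is only an operational detail.

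The pilot evidence also points away from a large problem. Section IV.D notes that the pilot did not show more falls, and the PAB Pilot Study section reports no adverse events in either group of 14. That pilot was small and began later in recovery, as outpatient therapy was ending, so it does not rule out a crossing.

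These points limit the size of the concern and make every week-level figure conditional. They leave one thing standing: the protocol states an interval for reporting injurious falls to the Safety Officer, that interval is a quarter, and nothing supplied states a shorter one.

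**Conclusion.** The concern holds as a minor point about reporting frequency. If the quarterly report is the route relied on, the Safety Officer could learn of a crossing up to about 13 weeks after it is on record, and about 6.5 weeks after on average. If the team already acts on session records, the gain from a change is small.

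The figures assume evenly spaced 13-week reports and a crossing at a random point between them. They do not show that the trial would run past its threshold for that long, because the route actually used and the chance of a crossing are both unknown. The saving of about 6 weeks should not be read as applying to the period after the last session. The thresholds are not at fault, and nothing here touches the efficacy analysis.

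**What to change.** In section IV.D, replace quarterly-only reporting of falls with the following:

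1. The treating therapist, who knows the arm from the content of the sessions, forwards each recorded fall to the Safety Officer within a few days, with arm and injury status. All falls are forwarded, because the 5-fall review counts more than injurious ones.
2. Falls after the last session are forwarded when the study team learns of them.
3. The Safety Officer keeps the by-arm count and tells the PI only that a review or a suspension is required.
4. The quarterly report and meeting continue, and both thresholds stay as they are.

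It would also help to say whether the triggers count every fall or only those judged study-related, since the sentence on study-related falls comes just before them.

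The cost is a few sentences, one message per fall, and somewhat more frequent contact with the Safety Officer. Blinding of the researchers who collect data is unaffected, because therapists already know the arm and the counts stay with the officer. A suspension notice still reveals a PAB excess, since the rule runs in one direction; that is inherent in the rule.

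The Statistical Analysis Plan is written in the past tense. If follow-up is already complete, the useful step is to confirm how the triggers were monitored and to carry this wording into later protocols.
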